STATISTICAL ANALYSIS PLAN

Risk Stratified Enhancements to Clinical Care: Targeting Care for Patients Identified Through Predictive Modeling as Being at High Risk for Suicide, with the Office of Mental Health Operations

SDR 16-195

NCT03280225

[name]
Principal Investigator

Funding Agency: HSR&D

Version 2.0

07/16/2021

Preface

The VHA predictive model identifies the top 5% of VHA patients at the highest predicted risk for suicide. These Veterans identified by VHA accounted for approximately 24% of all the suicide deaths, 37% of all reported suicide attempts, and 31% of inpatient psychiatric hospitalizations observed in VHA over the course of one year. Veterans in the highest 0.01% of the risk stratum had suicide rates 82 times greater than the rest of the sample in a development model.

Using this predictive model, VHA's Office of Mental Health and Suicide Prevention implemented a national suicide prevention outreach program entitled Recovery Engagement and Coordination for Health – Veterans Enhanced Treatment (REACH VET). REACH VET utilizes a dashboard to provide the names of patients identified by the model monthly to coordinators at each VA medical facility. REACH VET coordinators are responsible for notifying providers of the patient's status and prompting providers to re-evaluate care and take appropriate clinical steps if they are not already occurring (e.g., contacting the patient to re-engage in care, discussing potential changes in care with the patient).

Implementation assistance in the form of virtual external facilitation, an evidence-based implementation strategy, was offered to sites having difficulty implementing REACH VET during the system-wide rollout of the program. The analysis plan for specific aim 1b is below.

Scope and Analysis

Low performing VHA facilities were identified by leadership in seven Veteran Integrated Service Networks (VISN). Implementation assistance in the form of virtual external facilitation, an evidence-based implementation strategy, was offered to sites having using a stepped wedge design clustering sites at the VISN level. Two VISNs no longer needed facilitation by the time they reached the opportunity to receive it; these VISNs and facilities were excluded from any analyses. REACH VET Historic Summary Reports contain summary metrics used to evaluate facility performance on the four measures listed below.

REACH VET Outcome Measures

- Coordinator Assigned – the percentage of eligible Veterans who had a Coordinator assigned within a week of the monthly REACH VET scores being released. The denominator is the number of eligible Veterans within that week. The numerator is the number of Veterans with a record of a Coordinator assigned within or prior to that week.
- Provider Assigned – the percentage of eligible Veterans who had a Provider assigned within a week of the monthly REACH VET scores being released. The denominator is the number of eligible Veterans within that week. The numerator is the number of Veterans with a record of a Provider assigned within or prior to that week.

- Care Evaluation Performed – the percentage of eligible Veterans who had a care evaluation performed within a week of the monthly REACH VET scores being released. The denominator is the number of eligible Veterans within that week. The numerator is the number of Veterans with a record of a care evaluation performed within or prior to that week.
- Attempted Outreach – the percentage of eligible Veterans with a recorded attempted outreach within a week of the monthly REACH VET scores being released. The denominator is the number of eligible Veterans within that week. The numerator is the number of Veterans with a recorded attempted outreach within or prior to that week.

All outcomes data was collected from the Week 2 view of the REACH VET Historic Summary Report and encompasses days 1-14 after the release date.

Design Methods

Initial analysis design prescribed a stepped-wedge model clustering sites at the VISN level as depicted in figure 1.

| | Months | | | | | | | | | | | | | | | | | | | | | | | | | |
|---------------------|--------|---|---|---|---|---|---|---|---|----|----|--------------------|----|---------------------|----|----|----|----|----|----|----|----|----|----|----|--|
| | 1 | 2 | 3 | 4 | 5 | 6 | 7 | 8 | 9 | 10 | 11 | 12 | 13 | 14 | 15 | 16 | 17 | 18 | 19 | 20 | 21 | 22 | 23 | 24 | 25 | |
| Cluster A - 5 Sites | | | | | | | | | | | | | | | | | | | | | | | | | | |
| Cluster B - 4 Sites | | | | | | | | | | | | | | | | | | | | | | | | | | |
| Cluster C - 4 Sites | | | | | | | | | | | | | | | | | | | | | | | | | | |
| Cluster D - 6 Sites | | | | | | | | | | | | | | | | | | | | | | | | | | |
| Cluster E - 4 Sites | | | | | | | | | | | | | | | | | | | | | | | | | | |
| | | | | | | | | | | | | Pre-Implementation | | | | | | | | | | | | | | |
| | | | | | | | | | | | | | | Post-Implementation | | | | | | | | | | | | |

Figure 1. Study design assuming stepped wedge method at VISN level.

After initial sensitivity analysis (see section on Model fitting) it was determined that clustering at the VISN level lacked sufficient sample size compared to the quasi-experimental pre-post design as represented in figure 2.

[figure not shown]

Figure 2. Study design timeline assuming clustering within site.

Model Fitting

Pan (2001) proposed a quaslikelihood model-selection method for GEE under the independence model criterion (QIC). This criterion can also be used to select the best working correlation structure in GEE analyses (Cui, 2007).

Stepped Wedge within *CLUSTERS* QIC Scores

| Outcome | Independent | Autoregressive | Compound Symmetry | Unstructured |
|---------------------------|-------------|----------------|-------------------|--------------|
| Coordinator Accepted | 59.0 | 60.0 | 69.2 | NC |
| Provider Assigned | 86.0 | 86.3 | 92.6 | 36.6 * |
| Care Evaluation Performed | 89.8 | 89.7 | 93.5 | 45.1 |
| Outreach Attempted | 95.3 | 95.5 | 126.8 | NC |

NC – non-convergence, * Unstructured matrix is predominately negative on the pairs

Stepped Wedge within *SITES* QIC Scores

| Outcome | Independent | Autoregressive | Compound Symmetry | Unstructured |
|----------------------|-------------|----------------|-------------------|--------------|
| Coordinator Accepted | 57.3 | 56.9 | 60.07 | CE |

| | | | | |
|---------------------------|-------|-------|-------|----|
| Provider Assigned | 97.1 | 92.0 | 109.2 | CE |
| Care Evaluation Performed | 109.0 | 102.8 | 116.6 | CE |
| Outreach Attempted | 116.9 | 107.8 | 119.8 | CE |

CE – converged with error

6-month Pre-Post within SITES QIC Scores

| Outcome | Independent | Autoregressive | Compound Symmetry | Unstructured |
|---------------------------|-------------|----------------|-------------------|--------------|
| Coordinator Accepted | 38.2 | 38.6 | 37.5 | NC |
| Provider Assigned | 73.0 | 66.5 | 57.0 | NC |
| Care Evaluation Performed | 80.7 | 73.0 | 71.8 | NC |
| Outreach Attempted | 87.2 | 81.3 | 81.6 | NC |

Choose 6-month pre-post quasi-experimental model using compound symmetry correlation structure for observations within sites, time variable in months to account for secular trends, and a binary intervention variable (0,1) indicating study phase (pre-facilitation, post-facilitation).

Note, we do not model a transition period from pre-to-post Average number of implementation days = 175 (SD 49.3). Index date is based upon date of site visit.

Analysis

Our quasi-experimental pre-post intervention analysis evaluated four outcome measures as tracked by the REACH VET program across 23 VAMCs, during 6-month periods prior to implementation and again after the onset of implementation. We used the REACH VET Historic Summary Report to collect metrics for Coordinator assignment, Provider assignment, Care evaluation, and Attempted outreach all within one week of each monthly report's release date. To compare statistical differences in outcomes between pre-and post-periods we used generalized estimating equations (GEE) to control for clustering of observations within VAMCs. Fixed effects included a time-dependent variable identifying change in intervention status (pre-post) as well an independent variable of time to account for the possibility of improvement due to secular trends.

References

Cui, J. (2007). QIC Program and Model Selection in GEE Analyses. *The Stata Journal*:

Promoting Communications on Statistics and Stata, 7(2), 209–220.
<https://doi.org/10.1177/1536867X0700700205>

Pan, W. (2001). Akaike's information criterion in generalized estimating equations.
Biometrics, 57(1), 120–125. <https://doi.org/10.1111/j.0006-341x.2001.00120.x>

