For those identified as high risk, VHA's Office of Mental Health and Suicide Prevention developed a national suicide prevention outreach program entitled Recovery Engagement and Coordination for Health – Veterans Enhanced Treatment (REACH VET). REACH VET utilizes a dashboard to provide the names of patients identified by the model monthly to coordinators at each VA medical facility. REACH VET coordinators are responsible for notifying providers of the patient's status and prompting providers to re-evaluate care and take appropriate clinical steps if they are not already occurring (e.g., contacting the patient to re-engage in care, discussing potential changes in care with the patient).

To further strengthen REACH VET, treatment recommendations and/or augmentations are suggested. One recommendation is Caring Letters, an effective, low-cost suicide prevention intervention. Caring Letters involves the sending of recurring brief notes to patients at high risk expressing care and concern. It is one of the only psychosocial suicide prevention interventions that have reduced suicide mortality rates in a randomized controlled trial³⁻⁷. Despite positive results, Caring Letters have yet to become routine care – primarily because it requires considerable tracking to send letters. If these issues can be addressed, it is an ideal intervention to scale up for a large empirically defined high risk group.

REACH VET is currently being implemented in VHA. Additional implementation assistance in the form of virtual external facilitation, an evidence-based implementation strategy, will be offered to sites having difficulty implementing. VISNs will have the opportunity to receive facilitation for at least 4 of their facilities having difficulty implementing REACH VET; the REACH VET Program Manager will discuss this with VISN leadership, who will decide if they want to participate in facilitation. Participating VISNs will be randomized to when their VISN will receive facilitation.

The VA Serious Mental Illness Treatment, Resource, and Evaluation Center (SMITREC) and Partnered Evidence-Based Policy Resource Center (PEPRc) are conducting a summative evaluation of REACH VET's impact on Veteran outcomes using VHA databases. The current study extends the breadth and depth of their evaluation with these specific aims.

Specific Aim 1: Evaluate the impact of virtual external facilitation versus standard implementation.

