METHODS

Overview of Evaluation Methods

This evaluation will utilize a mixed methods approach. To evaluate our aims, the project will utilize a stepped wedge controlled trial design. This design staggers the timing of providing implementation support and allows every participating VISN to receive the implementation support. The unit of intervention in this study is the site and randomization will occur at the VISN level for virtual external facilitation. Using a balancing algorithm for facility size, suicide admissions, and rural vs. urban status, sites will be randomized to when virtual facilitation will occur. Below we describe the conceptual models, national implementation plan, clinical interventions, and implementation strategy, followed by the design, outcomes, and analysis for each specific aim.

Project Management

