[name]	Yes	No	Yes	No	Yes	No	No

Data Use Agreements (DUAs)

A data use agreement was finalized with the Office of Mental Health Operations (OMHO). This DUA covers the REACH VET dashboard data being sent to the evaluation team. This data includes: names of patients identified by REACH VET and their information as displayed in the dashboard and actions taken by the REACH VET coordinator and providers.

Table 2: REACH VET Dashboard Variables for Data Collection

Patient Level Variables:
First Name
Last Name
Last 4 of SSN
Facility (location)
Date First Showed up on Dashboard
Coordinator Level Variables:
First Name

Last Name

Is there a High Risk Suicide Flag documented in CPRS?

Dates - Coordinator:

Received name of patient

Identified a primary patient provider

Notified provider of the specific patient and program requirements

Asked provider to re-evaluate patient's care

Provider Level Variables:

First Name

Last Name

Dates - Provider:

Received notification from REACH VET coordinator about the patient

Reviewed current diagnoses and treatment plan

Indicated enhanced care options:

Caring Communications

Safety Planning

Increased monitoring of stressful life events

Improve coping skills

Other

Care was reviewed and no changes are clinically indicated at this time

Informed Veteran that they have been identified as being at risk

Discussed care enhancement options with the Veteran

Discussed treatment plan changes with the Veteran

Indicated that outreach attempts have been made but provider unable to get in touch with the Veteran

Indicated that no outreach to Veteran is clinically indicated at this time

NATIONAL IMPLEMENTATION PLAN

Clinical Intervention: REACH VET

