The plan for national roll out of REACH VET was developed by OSP, with input from the evaluation team and other partners. National implementation of REACH VET began in November 2016 and included identification of a REACH VET coordinator at each facility, REACH VET dashboard training for coordinators and interested providers, and rollout of the dashboard. Each facility initially received the top eight names of patients identified as being in the top 0.1% of risk for suicide at that facility. Over the following three months, facilities will receive additional names via the dashboard until all patients in the top 0.1% have been identified; facilities can opt to receive the full list at any time. Standard implementation strategies will include training and education, chart note templates to support documentation, an intranet site of resources for coordinators and providers, technical assistance as requested, and clinical consultation as requested. Barriers and facilitators will be assessed during this time by the evaluation team.

Figure 2. Trial design.

		Study Month							
Network	Sites	1-3	3 – 6	6 - 9	9 - 12	12 - 15	15 - 18	18 - 21	21 - 24
A	1-4	Facilitation							
B	5-8	Awaiting Facilitation		Facilitation					
C	9-12	Awaiting Facilitation		Facilitation					
D	13-16	Awaiting Facilitation			Facilitation				
E	17-20	Awaiting Facilitation				Facilitation			
F	21-24	Awaiting Facilitation					Facilitation		
G	25-28	Awaiting Facilitation						Facilitation	

Virtual

External Facilitation Implementation Strategy

Additional implementation support will begin in April 2017. We will target 7 networks and 4 sites in each network not meeting the criterion for timely notification. The participating VISNs will be randomized to when the sites in their network will receive facilitation.

The facilitators will be two master’s level and one doctoral level clinicians with clinical expertise in suicide prevention and REACH VET; the facilitators are funded through OSP and are not part of the evaluation team. They attended facilitation training February 1-2, 2017. The training included how to conduct virtual facilitation and utilized a virtual external facilitation manual developed by a workgroup of the Behavioral Health QUERI’s Implementation Facilitation Learning Collaborative.

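### Two of seven VISNs are dropped after randomisation because they no longer needed help at their turn, with no stated rule and no analysis that keeps them

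*SAP*

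**What the plan says.** **Entry and timing.** Protocol, Evaluation Objectives, offers facilitation to VISNs with struggling facilities: "the REACH VET Program Manager will discuss this with VISN leadership, who will decide if they want to participate in facilitation". Timing is then left to chance. Under Virtual External Facilitation Implementation Strategy: "The participating VISNs will be randomized to when the sites in their network will receive facilitation". Specific Aim 1b, Design, says the same. The Overview of Evaluation Methods gives as a merit of the design that it "allows every participating VISN to receive the implementation support".

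**Need.** The only criterion in either document is timely provider notification. The facilitation section uses it to select sites, and Aim 1b, Design, gives it as an example with figures (80% of notifications within 7 days in the last month). Both uses concern entry. Notification has its own entry among the dashboard variables in Table 2 ("Notified provider of the specific patient and program requirements") and is not one of the four outcomes.

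**Removal.** SAP, Scope and Analysis, starts from seven VISNs and then reports: "Two VISNs no longer needed facilitation by the time they reached the opportunity to receive it; these VISNs and facilities were excluded". The sentence ends by extending this to all analyses ("these VISNs and facilities were excluded from any analyses").

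**What is analysed.** SAP Figure 1 shows five clusters. The final model (SAP, Model Fitting and Analysis) compares six months before with six months after the index date at 23 facilities, using GEE with a phase indicator and a time term in months. The index date comes from the site visit. No model listed in the SAP includes the two VISNs.

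**The concern.** An exclusion made when a VISN reaches its turn comes after the randomised schedule was set, and it can only affect VISNs that had to wait. The stated reason is that help was no longer needed without facilitation having been given. If that judgement followed the outcomes, the plan removes VISNs that did well while waiting and keeps those that did not.

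The chosen pre-post model separates facilitation from background improvement only through its time term. Selection on recent performance can affect it in two ways. The retained VISNs may sit temporarily low before their index date and regress upwards afterwards. The time trend is also fitted without VISNs that may have improved without help. Both would be credited to facilitation.

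At stake is whether the 23-site result depends on leaving the two VISNs out, and to whom it applies. Nothing in the plan lets a reader check either.

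**Working it through.** **1. Counts.** SAP Figure 1 gives 5 + 4 + 4 + 6 + 4 = 23 sites, which reproduces the 23 facilities in SAP, Analysis. VISNs: 7 − 2 = 5, so 2/7 = 29% are missing. The protocol planned 7 × 4 = 28 sites. The SAP does not give the two VISNs' site counts. The protocol speaks of "VISNs will have the opportunity to receive facilitation for at least 4 of their facilities having difficulty implementing REACH VET". If that held for them, at least 2 × 4 = 8 sites are lost and at most 23/(23 + 8) = 23/31 = 74% are kept.

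**2. Is there a rule?** Entry text: leadership decides on participation, and sites are chosen on timely notification. Removal text: only the SAP sentence above. Neither document says who re-judges need, when, on what data, or what becomes of a VISN that improves while waiting. Aim 1b, Measures, describes the four outcomes as the metrics by which a facility's implementation is tracked. A link between need and outcomes is therefore plausible but undocumented.

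**3. Size of a conditional bias.** The documents give no variances, trends or data for the two VISNs, so every input here is an assumption:
- Seven VISNs with a true effect of 0 and steps every 3 months. Retained VISNs have 5, 4, 4, 6 and 4 sites; each dropped VISN has 4.
- SDs: VISN 6, site 5, monthly noise 8 points.
- Background over 24 months: a linear VISN trend (mean 20, SD 10, or mean 30, SD 15), or the first of these plus autocorrelated VISN drift of SD 6 or 12.
- Exit when the VISN's last-month mean, or its 3-month mean plus judgement noise (SD 8), reaches 80; or two waiting VISNs leave at random. Results are for replicates with exactly two exits.
- Model: 6 + 6 months, exchangeable correlation, phase and linear time.

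The SAP does not say whether its months run from the index date or by calendar, so both were fitted. Bias of the retained-only pre-post estimate, in percentage points:

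| Exit judged on | Months from index | Calendar months | Settings above 2 Monte Carlo SE (index / calendar) | Largest bias in SDs of the estimate (index / calendar) |
|---|---|---|---|---|
| the outcome itself | +0.1 to +1.6 | +0.8 to +2.6 | 13 / 16 of 16 | 0.33 / 0.71 |
| a metric correlated 0.5 | −0.1 to +1.1 | +0.3 to +1.4 | 7 / 16 of 16 | 0.22 / 0.33 |
| a metric correlated 0.3 | 0.0 to +0.4 | +0.2 to +0.8 | 3 / 13 of 16 | 0.11 / 0.20 |
| chance (8 settings, SE up to 0.18) | −0.1 to +0.4 | −0.1 to +0.2 | – | – |

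The SD of the estimate was 1.8 to 5.4 points. Under random exit, the paired difference from the all-seven fit was −0.1 to +0.1. Two further simulations with other assumed inputs gave +0.2 to +0.6 and +0.3 to +0.4 points (SE 0.12 to 0.19 for the latter) for exit on the outcome.

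**4. The stepped wedge.** With only the retained VISNs, performance-based exit gave −1.6 to +1.3 points, so there is no consistent direction. With all seven coded by scheduled step it was near zero: −0.3 to +0.2 (SE up to 0.22).

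**5. Control-only coding.** Keeping the two VISNs but coding them as control throughout gave −1.0 to −1.8 points under no true effect. Which VISNs stay control is then itself decided by performance, so the selection returns with the opposite sign.

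**6. Dilution.** If two of seven VISNs are scheduled but not facilitated, equal weighting keeps 5/7 = 71% of the effect, and weighting by site keeps 23/31 = 74%. With 10 points added to the five facilitated VISNs, the simulated fits kept 65% to 81% (stepped wedge 65% to 74%). At 74% the estimate falls by 10 × (1 − 0.74) = 2.6 points with no selection bias at all, as much as the largest bias in step 3.

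**The case against.** The exclusion is disclosed with number, timing and reason. The final analysis is called quasi-experimental and claims no randomised contrast. Facilitation was an offer aimed at sites in difficulty, so leaving out VISNs no longer in difficulty fits that aim. VISNs that were never facilitated presumably have no site-visit date and cannot enter the pre-post model as defined. The only documented need criterion is notification, so the lower rows of the table are closer to the text than the first. The SAP already reports fitted models, so any new analysis is post hoc. A diluted estimate would be smaller with or without bias.

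Most of this stands, and it limits the point. The 23-site analysis can remain as defined, the added one must be labelled post hoc, and a smaller seven-VISN estimate cannot by itself measure bias. But disclosure supplies no rule, no data and no check. Using the two VISNs as control-only data looks more direct, but step 5 shows that it brings in its own bias. Coding by scheduled step does not depend on the exclusion under no effect, so it is a valid test of that hypothesis.

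A reader might infer that the exclusion has inflated the result, or that any correlation between need and outcome is enough to do so. The documents do not support the first: they do not say what need was judged on. The second fails with months from index, where most settings showed no clear tilt (7 and 3 of 16 did).

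**Conclusion.** The point holds and should be fixed, with medium confidence. It is certain from the text that 2 of 7 VISNs (29%) leave every analysis after a randomised schedule, without a stated rule, and that all SAP models rest on the remaining 23 sites. The protocol is the source for randomisation; the SAP says only that the design was a stepped wedge.

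The bias is conditional. If need was judged on the outcomes, the pre-post estimate can be tilted towards facilitation. If it was judged on a correlated metric, a tilt is possible but not consistently shown when time runs from the index date. If it was unrelated, the bias is near zero. Under the assumed threshold, correlations, trends and SDs, the bias is small against the SD of the estimate. The true size cannot be found from the documents.

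Two further inferences should be avoided. No direction can be claimed for the stepped-wedge models. Nor is it shown that restoring the two VISNs would have cured the lack of sample size that the SAP gives as its reason for leaving VISN-level clustering.

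**What to change.** In SAP, Scope and Analysis, replace the blanket exclusion with wording such as: *not in the 23-site pre-post analysis, but included in a sensitivity analysis of all seven VISNs by randomised scheduled step (control before it, facilitation from it on, whether or not delivered), using the same Historic Summary Reports.*

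- Fit this in the stepped-wedge model. Label it post hoc and as the effect of being scheduled for facilitation.
- Use it as a test of no effect that does not depend on the exclusion. State that its estimate is diluted (to about 65% to 81% under the assumptions here), so that a smaller value alone does not show bias in the 23-site result.
- Do not code the two VISNs as control-only.
- Show their site counts and monthly values on the four outcomes beside the other five VISNs.
- Limit the 23-site conclusion to VISNs still judged to need facilitation at their turn.

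Saying who judged need, when and on what data, and from which origin the months are counted, would be useful reporting, but would not by itself settle the point.

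The cost is one more data pull, one added analysis and a table. The downside is a diluted estimate that answers a different question, so it sits beside the 23-site analysis and does not replace it.

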Measures: We will assess the impact of facilitation on REACH VET implementation using the four outcome measures as tracked by the REACH VET program. We will use the REACH VET Historic Summary Report to collect data for Coordinator assignment, Provider assignment, Care evaluation, and Attempted outreach all within one week of each monthly report's release date. These metrics are those tracked to determine a facility's implementation of REACH VET. They are defined as:

- Coordinator Assigned – the percentage of eligible Veterans who had a Coordinator assigned within a week of the monthly REACH VET report being released. The denominator is the number of eligible Veterans within that week. The numerator is the number of Veterans with a record of a Coordinator assigned within or prior to that week.
- Provider Assigned – the percentage of eligible Veterans who had a Provider assigned within a week of the monthly REACH VET report being released. The denominator is the number of eligible Veterans within that week. The numerator is the number of Veterans with a record of a Provider assigned within or prior to that week.
- Care Evaluation Performed – the percentage of eligible Veterans who had a care evaluation performed within a week of the monthly REACH VET report being released. The denominator is the number of eligible Veterans within that week. The numerator is the number of Veterans with a record of a care evaluation performed within or prior to that week.
- Attempted Outreach – the percentage of eligible Veterans with a recorded attempted outreach within a week of the monthly REACH VET report being released. The denominator is the number of eligible Veterans within that week. The numerator is the number of Veterans with a recorded attempted outreach within or prior to that week.

Analysis: To compare statistical differences in outcomes between pre- and post-facilitation periods we will use generalized estimating equations (GEE) to control for clustering of observations within VAMCs. Fixed effects included a time-dependent variable identifying change in intervention

status (pre-post) as well as an independent variable of time to account for the possibility of improvement due to secular trends.

Specific Aim 1c: Collect the costs of the REACH VET and Caring Letter interventions and of the virtual external facilitation strategy for subsequent analysis of potential cost effectiveness.

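### The SAP's reason for replacing the stepped wedge with a 6-month pre-post model does not cover the stepped wedge it fitted within the same 23 sites, and QIC cannot fill the gap

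*SAP*

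**What the plan says.** The protocol (Overview of Evaluation Methods; Virtual External Facilitation Implementation Strategy; Specific Aim 1b) sets out a stepped wedge in which VISNs are randomised to when facilitation starts. Its Aim 1b analysis reads: "To compare statistical differences in outcomes between pre- and post-facilitation periods we will use generalized estimating equations (GEE) to control for clustering". The clusters there are the VAMCs, and the model has a pre/post status term and one time term. It mentions no 6-month window.

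The SAP (Design Methods) states: "Initial analysis design prescribed a stepped-wedge model clustering sites at the VISN level as depicted in figure 1". Seven VISNs were identified, but "Two VISNs no longer needed facilitation by the time they reached the opportunity to receive it", which leaves five VISNs and 23 sites. After Figure 1 the SAP says that "it was determined that clustering at the VISN level lacked sufficient sample size compared to the quasi-experimental pre-post design" and refers the reader to Model Fitting.

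Model Fitting introduces QIC as a model-selection criterion. It then gives three QIC tables: stepped wedge within clusters, stepped wedge within sites, and 6-month pre-post within sites. It concludes: "Choose 6-month pre-post quasi-experimental model using compound symmetry correlation structure for observations within sites". The model carries a "time variable in months to account for secular trends" and a binary status variable. A note gives a mean implementation period of 175 days (SD 49.3) and adds: "Index date is based upon date of site visit". The Analysis section describes 23 VAMCs "during 6-month periods prior to implementation and again after the onset of implementation".

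**The concern.** The stated reason is about sample size at VISN level. The cited section contains no standard error, interval width, power, ICC or minimum number of clusters. The reason also applies to only one of the two stepped-wedge fits shown. The other is clustered within sites, as the pre-post model is, and the SAP says nothing specific about why it was not used.

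Aim 1b compares facilitation with standard implementation during a national rollout, when all sites may be improving. Same-month contrasts between VISNs already facilitated and VISNs still waiting are what the randomised start times protect. Six-month windows drop some of those contrasts. A restriction chosen after fits to all four outcomes were in hand needs a valid stated reason. The single time term is a second, separate weakness: if improvement was not linear, part of it is credited to facilitation.

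**Working it through.** **1. Sites.** Figure 1 lists 5 + 4 + 4 + 6 + 4 = 23, which matches the 23 VAMCs in the Analysis section. The site-level stepped wedge and the pre-post model therefore have the same 23 clusters; the VISN-clustered model has 5.

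**2. Rows (inferred; the SAP prints no counts).** Stepped wedge: up to 23 × 25 months = 575 site-months. Pre-post: at most 23 × 12 = 276. Ratio 276/575 = 48%.

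**3. Convergence.** In the site-level stepped-wedge table, independence, autoregressive and compound symmetry have scores for all four outcomes; unstructured converged with error for all four. In the pre-post table the same three have scores and unstructured did not converge for any outcome. Convergence does not separate the two.

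**4. QIC, stepped wedge within sites → pre-post (fall = 1 − pre-post/stepped wedge).**

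| Outcome | Independence | Autoregressive | Compound symmetry |
|---|---|---|---|
| Coordinator | 57.3 → 38.2 (33%) | 56.9 → 38.6 (32%) | 60.07 → 37.5 (38%) |
| Provider | 97.1 → 73.0 (25%) | 92.0 → 66.5 (28%) | 109.2 → 57.0 (48%) |
| Care evaluation | 109.0 → 80.7 (26%) | 102.8 → 73.0 (29%) | 116.6 → 71.8 (38%) |
| Outreach | 116.9 → 87.2 (25%) | 107.8 → 81.3 (25%) | 119.8 → 81.6 (32%) |

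Pre-post is lower in 12 of 12 cells. But QIC is built from a sum over observations, and the inferred rows fall by 52%. Divided by inferred rows, the order reverses in all 12 cells; for care evaluation, autoregressive, 102.8/575 = 0.179 against 73.0/276 = 0.264. That ratio is not a valid test of fit either. It shows only that the raw ranking follows the row count. In simulated data with one model for all months, cutting to 276 rows lowered QIC in 400 of 400 runs, with median falls of 50-52%.

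**5. Choice of working correlation.** Among the three simpler structures, compound symmetry has the highest QIC in 8 of 8 stepped-wedge rows (clusters and sites) and the lowest in 3 of 4 pre-post rows; for outreach, autoregressive is lower (81.3 against 81.6). The selected structure depends on the row set. Nor does raw QIC favour pre-post throughout: the VISN-clustered unstructured fit is lower for care evaluation (45.1 against 71.8) and, with the footnote about negative pairs, for provider assignment (36.6 against 57.0).

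**6. Single month term.** Assumptions: Figure 1's shading is unreadable, so VISN starts were set at months 7/10/13/16/19, 7/10/14/17/20, 7/9/11/13/15 or 4/7/10/13/16, so that every VISN has at least three pre-months. True effect 0; exchangeable correlation 0.1-0.9; a common trend either saturating from 40% towards 80% (half-time 3, 6 or 9 months) or a single 10-point jump in any of months 2-25. Expected coefficient for facilitation status, in percentage points:

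| Model | False effect |
|---|---|
| Pre-post, one month term (calendar or index-relative) | -1.4 to +2.1 |
| Stepped wedge, all months, one calendar-month term | -4.1 to +4.7 |
| Either row set, calendar-month effects | 0.0 |

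Calendar-quarter effects come close, but are exact only when starts fall on quarter boundaries. The time term, not the window, produces the false effect.

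**7. Critical value.** With t on VISNs minus 2 degrees of freedom (assumed), 5 − 2 = 3 df gives 3.18, and 3.18/1.96 = 1.62.

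**The case against.** The strongest case for the SAP has several parts.

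- **A reason can be inferred.** QIC is introduced as a selection method and pre-post is lower in every comparable cell. That is a basis of sorts, but step 4 shows it is not valid across row sets.
- **The protocol already has a pre/post GEE within VAMCs and one time term.** This stands. Relative to that text the new element is the 6-month restriction, and the time-term weakness is inherited.
- **Six months has a visible basis.** The 175-day mean implementation period is about 5.75 months. This also stands, although the SAP does not make the link. A transient effect favours the window: with a 10-point effect lasting six months and then vanishing, a calendar-month stepped wedge on all months returned 7.5 to 11.9 under the assumed starts and correlations, while pre-post returned 10.0.
- **Five VISNs are few.** In illustrative null simulations, uncorrected z tests rejected 19-24% of the time, and the Mancl-DeRouen correction with t on 3 df only 1.5-2.6%. VISN-level inference has a price, and the correction must be named.
- **The model is openly called quasi-experimental**, so the SAP does not present the estimate as randomised.

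Three stronger readings are tempting and not supported. A reader might infer that the SAP omits how site-visit dates relate to randomised starts and whether month is calendar or index-relative; Figure 2, the site-level timeline, is not shown in the available text and may contain both. A reader might infer that pre-post is badly biased because the first VISN had no pre-months; the documents put rollout in November 2016 and facilitation in April 2017, and describe 6-month pre-periods. A reader might infer that the window itself introduces bias; step 6 shows a stepped wedge with one month term has the wider range.

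**Conclusion.** The point holds as a defect of justification and of the time term. The sample-size reason cannot exclude the site-level stepped wedge, which has the same 23 clusters and apparently about twice the rows, and the QIC difference cannot rank the two designs. This part needs only the printed tables and the inferred row counts. The size of the time-term problem, about -1.4 to +2.1 points for the chosen model, rests on assumed start months, trends and correlations and on no true effect.

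It does not follow that a VISN-clustered stepped wedge must become the sole primary analysis. With five VISNs that is a trade-off on which statisticians would differ. Nor would it fully restore the randomised comparison, because which VISNs remained depended on when their turn came. The plan should be corrected, but the pre-post result need not be discarded.

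**What to change.** In SAP Design Methods and Model Fitting:

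1. Use QIC only to choose the working correlation within one data set. Delete both QIC and the sample-size statement as grounds for preferring pre-post to the site-level stepped wedge. Print the number of rows behind each table.
2. Replace the single month term with calendar-month effects, or calendar-quarter effects if months are too sparse, and re-check the working correlation afterwards.
3. Beside the pre-post result, report a stepped-wedge GEE on all available site-months, with status switched on at each VISN's randomised start. Base inference on VISNs, with a named small-sample correction and t critical values. State plainly that the 6-month pre-post estimate is non-randomised.
4. Give the reason for the 6-month window in terms other than QIC, for example the 175-day mean implementation period if that was the basis.

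The cost is SAP rewording and some re-analysis of monthly reports already held. It is more than a re-run, since the time effects, switch date and level of inference may differ from the fits shown. Intervals will probably be wider: the critical value alone is 62% above 1.96 at 3 df. The all-months model also assumes the effect persists after facilitation ends, so the 6-month result remains useful if the effect is transient.
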